5.7. Measurements of Treatment Compliance

Percent compliance will be summarized using the Safety Set and listed. Compliance is calculated as follows: Compliance (%) = total number of study infusions taken / total number of expected infusions, multiplied by 100.

The number and percentage of participants who had a percentage of drug compliance range by increment of 10% (<80%, $\geq 80\%$ - <90%, ≥ 90 - $\leq 100\%$, and >100%) will also be summarized.

5.8. Protocol Deviations

All protocol deviations will be reviewed and documented before database lock. Protocol deviations are being captured in accordance with the protocol deviation management plan. They may also be identified through programmable checks of the data.

The CRO/Apellis will classify major and minor protocol deviations per the agreed Protocol Deviation Handling Plan. The Apellis study team will review the protocol deviations and their classification throughout the study and before database lock.

The number and percentage of participants with protocol deviations will be summarized by importance of deviation for ITT Set and listed.

6. EFFICACY ANALYSES

Efficacy analysis including primary, key secondary, additional secondary, and exploratory analysis will be performed primarily using the ITT set, with participants grouped according to the treatment assigned at randomization. Available data from all randomized participants regardless of adherence to the protocol will be included in the efficacy analysis, this includes data from participants who discontinued study drug early but continued with study assessments. All efficacy data will be listed for the ITT set.

All statistical tests will be performed at 2-sided 5% level of significance and all confidence intervals will be two-sided 95% confidence intervals.

Unless otherwise noted, the following randomization stratification factors will be adjusted for in analysis of efficacy endpoints in the overall population:

- Participants with posttransplant recurrence versus nontransplant participants
- Participants with baseline renal biopsies versus participants without baseline renal biopsies

If participants are found to have had the incorrect stratum assigned at randomization, they will be analyzed according to the randomization stratum.

For potential treatment imbalance, will check imbalance between treatment and placebo. In case there are major imbalances on important prognostic factors other than those already included in the analysis model, additional sensitivity analyses may be performed to adjust any or all of these factors if appropriate. Data will be verified for outliers. Sensitivity analyses may be performed using more robust approaches or excluding outliers.

6.1. Analysis Models

In general, data will be analyzed using the approaches described below.

Mixed-effect model for repeated measures (MMRM) for continuous outcomes

Longitudinal assessments for changes from baseline in continuous outcomes will be analyzed using a mixed-effect model for repeated measures (MMRM). The model will include fixed categorical effects for treatment group, visit, disease type (C3G vs. IC-MPGN), baseline immunosuppressants use (yes vs. no, to add this effect for primary endpoint analysis only), stratification factors, and the visit-by-treatment group interaction, as well as the continuous, fixed covariate of the baseline value of the endpoint. The least square (LS) means with standard errors (SEs) and 95% confidence intervals (CIs) of the change from baseline will be presented by treatment group and visit; between-treatment differences and 95% CIs and p-values will be presented by visit. LS means (±SE) will be plotted over time by treatment group.

A common unstructured covariance matrix will be used. If the model fails to converge, the following covariance structures will be fit in this order until convergence is met: (*i*) heterogenous autoregressive ARH(1), (*ii*) autoregressive AR(1), (*iii*) compound symmetry CS. The sandwich estimator (Diggle et al. 1994) will be used to estimate the standard errors of the fixed effects parameters.

Logistic regression model for binary outcomes

Binary outcomes will be analyzed using a logistic regression model. The model will include treatment group as independent variable and adjusted for baseline value of the variable(s) used to define the endpoint, disease type, and stratification factors. Point estimates for proportions and difference in proportions will be presented. The p-value and odds ratio of being a responder for the pegcetacoplan group to being a responder for the placebo group with associated 95% CI will be provided. In situations where event rates are low leading to convergence issue for the logistic regression model, alternative methods such as removal of covariates may be considered when appropriate.

Analysis of covariance (ANCOVA)

Analysis of covariance (ANCOVA) will be used to analyze C3G histologic index activity score, FACIT-Fatigue score, and KDQOL score with treatment as a fixed effect, adjusted for baseline score of the endpoint, disease type, and stratification factors. LS means will be presented for each treatment group, along with the between-treatment difference and 95% CI.

Mixed effects model for slope analysis of continuous outcomes

For slope analysis of continuous outcomes, a mixed effects model using the baseline and all postbaseline assessments will be used and will include treatment group, disease type, baseline immunosuppressants use (to add this effect for primary endpoint analysis only), and stratification factors as fixed effects, time (study week, continuous assuming linearity), and the time-by-treatment interaction. A common unstructured covariance matrix will be used. If the model fails to converge, the following covariance structures will be fit in this order until convergence is met: (*i*) heterogenous autoregressive ARH(1), (*iii*) autoregressive AR(1), (*iii*) compound symmetry CS. The sandwich estimator (Diggle et al. 1994) will be used to estimate the standard errors of the fixed effects parameters.

6.2. Multiplicity Adjustment

The primary endpoint of the study will be tested at the 2-sided 0.05 level, and if the null hypothesis for the primary endpoint is rejected, the secondary endpoints will be tested. The key secondary and additional secondary endpoints will be tested sequentially in the order in which they are presented in Section 2.2.2 and Section 2.2.3; the testing will stop once a null hypothesis is not rejected. This fixed-sequence testing procedure will ensure that trial-wise error rate is controlled to be 0.05.

6.3. Estimands

The primary objective of this study is to assess the efficacy of twice-weekly SC doses of pegcetacoplan compared with that of placebo in patients with primary C3G or IC-MPGN on the basis of a reduction in proteinuria.

The estimands and their attributes for the primary and all comparative key secondary and additional secondary endpoints are shown in Table 1 below. This includes strategies for addressing the following intercurrent events (ICEs):

- ProhibiRescue = use of prohibited concomitant medication specified in Protocol Section 8.3.3, or use of rescue therapies defined in Protocol Section 8.3.2
- RenalReplace = start renal replacement therapy (dialysis and/or renal transplant)
- DisctTrt = permanent discontinuation of study treatment

Table 1: Estimands and Attributes for Primary, Key Secondary, and Additional Secondary Endpoints

Socona	Secondary Endpoints				
For all estimands: A. Population: participants with C3G or IC-MPGN defined through the study inclusion/exclusion criteria in the ITT Set B. Treatment regimens of interest: • Twice-weekly SC doses of pegcetacoplan for 26 weeks of treatment • Twice-weekly SC doses of placebo for 26 weeks of treatment					
C: Variable (or endpoint) D: Strategies for addressing ICEs (event†: strategy‡) E: Population-level sum					
Primary Estimand					
Log-transformed ratio of uPCR at week 26 compared to baseline	ProhibiRescue: hypothetical strategy RenalReplace: hypothetical strategy DisctTrt: treatment policy strategy	Difference in mean change of log-transformed uPCR from baseline to week 26 (measured by equal-weighted average over weeks 24, 25, and 26) between the pegcetacoplan group and the placebo group.			
Key Secondary Estimands	(for comparative endpoints)				
The proportion of participants who meet the criteria for achieving a composite renal endpoint at week 26	ProhibiRescue, RenalReplace, DisctTrt: composite strategy	Odds ratio of achieving a composite renal endpoint for the pegcetacoplan group to achieving a composite renal endpoint for the placebo group at week 26.			
The proportion of participants with a reduction of at least 50% from baseline in uPCR at week 26	ProhibiRescue, RenalReplace, DisctTrt: composite strategy	Odds ratio of achieving a reduction of at least 50% from baseline in uPCR for the pegcetacoplan group to achieving a reduction of at least 50% from baseline in uPCR for the placebo group at week 26.			
For participants with evaluable renal biopsies, the change from baseline in the activity score of the C3G histologic index score at week 26	ProhibiRescue: hypothetical strategy RenalReplace: hypothetical strategy DisctTrt: treatment policy strategy	Difference in mean change from baseline to week 26 in activity score between the pegcetacoplan group and the placebo group.			

Table 1: Estimands and Attributes for Primary, Key Secondary, and Additional Secondary Endpoints

The proportion of participants with evaluable renal biopsies showing decreases in C3c staining on renal biopsy from baseline at week 26	ProhibiRescue, RenalReplace, DisctTrt: composite strategy	Odds ratio of showing decreases in C3c staining for the pegcetacoplan group to showing decreases in C3c staining for the placebo group at week 26.
Change from baseline in eGFR at week 26	ProhibiRescue: hypothetical strategy RenalReplace: hypothetical strategy DisctTrt: treatment policy strategy	Difference in mean change of eGFR from baseline to week 26 between the pegcetacoplan group and the placebo group.
Additional Secondary Est	imands (for comparative endpoints)	
The proportion of participants achieving proteinuria <1 g/day at week 24	ProhibiRescue, RenalReplace, DisctTrt: composite strategy	Odds ratio of achieving proteinuria <1 g/day for the pegcetacoplan group to achieving proteinuria <1 g/day for the placebo group at week 24.
For participants with serum albumin levels below LLN at baseline, the proportion of participants with normalization of serum albumin levels at week 26	ProhibiRescue, RenalReplace, DisctTrt: composite strategy	Odds ratio of achieving normalization of serum albumin for the pegcetacoplan group to achieving normalization of serum albumin for the placebo group at week 26.
For participants with serum C3 levels below the LLN at baseline, the proportion of participants with serum C3 levels above the LLN at week 26	ProhibiRescue, RenalReplace, DisctTrt: composite strategy	Odds ratio of achieving serum C3 levels above the LLN for the pegcetacoplan group to achieving serum C3 levels above the LLN for the placebo group at week 26.
The change from baseline in FACIT–Fatigue Scale score	ProhibiRescue: hypothetical strategy RenalReplace: hypothetical strategy DisctTrt: treatment policy strategy	Difference in mean change from baseline to week 26 in FACIT-Fatigue Scale score between the pegcetacoplan group and the placebo group.
The change from baseline in KDQOL score	ProhibiRescue: hypothetical strategy RenalReplace: hypothetical strategy DisctTrt: treatment policy strategy	Difference in mean change from baseline in KDQOL score between the pegcetacoplan group and the placebo group.

Table 1: Estimands and Attributes for Primary, Key Secondary, and Additional Secondary Endpoints

†ICE definitions:

- ProhibiRescue = use of prohibited concomitant medication specified in Protocol Section 8.3.3, or use of rescue therapies defined in Protocol Section 8.3.2
- RenalReplace = start renal replacement therapy (dialysis and/or renal transplant)
- DisctTrt = permanent discontinuation of study treatment

‡Strategies:

- Composite strategy: the endpoint status at or after the initiation of the ICEs will be regarded as non-responder.
- Hypothetical strategy: (for ICEs due to ProhibiRescue) all measurements after the ICEs will be set to
 missing. Missing data resulting from the ICEs will be imputed using copy reference imputation.
 (for ICEs due to RenalReplace) all measurements after the ICEs will be set to missing. Missing data
 resulting from the ICEs will be imputed based on the worst change of all participants across visits plus a
 random error.
- Treatment policy strategy: all measurements after the ICEs will be used as is. Missing data resulting from the ICEs will be imputed using copy reference imputation.

6.4. Analyses of Primary Efficacy Endpoint

The primary efficacy endpoint is the log-transformed ratio of uPCR at week 26 compared to baseline. The null $(H_{1,0})$ and alternative $(H_{1,1})$ hypotheses for the primary efficacy analysis are:

- H_{1,0}: There is no difference in log-transformed ratio of uPCR at week 26 compared to baseline between the pegcetacoplan and placebo treatment groups.
- H_{1,1}: There is a difference in log-transformed ratio of uPCR at week 26 compared to baseline between the pegcetacoplan and placebo treatment groups.

uPCR values are expected to be highly skewed so that the values will be natural log-transformed in analysis and presentation. For the primary efficacy endpoint, sensitivity analyses (Section 6.4.2), supplemental analyses (Section 6.4.3), and subgroup analyses (Section 6.4.4) will be performed.

6.4.1. Main Analysis of Primary Efficacy Endpoint

The primary endpoint will be analyzed in the ITT set with participants grouped according to the treatment assigned at randomization.

Baseline uPCR value will be calculated as the average of the uPCR measurements from at least 6 of the 9 first-morning spot urine (FMU) samples collected between the start of screening and day 1, inclusive. The uPCR values used to calculate baseline should include those from the samples collected on day -2, day -1, and before dosing on day 1. In situations where less than 6 samples or more than 9 samples were collected, the average of all collected samples will be used for baseline derivation. For scheduled visits where 3 collections are expected for calculating averages, if there are missing collections, the average will be based on those available collections; if there are more than 3 collections available (e.g., additional unscheduled collections), the selection of 3 collections to be used for average calculation will follow data handling conventions as specified in Section 13.4.

An MMRM model will be used to analyze the primary endpoint. The model will include fixed categorical effects for treatment group, visit, disease type (C3G vs. IC-MPGN), baseline immunosuppressants use (yes vs. no), stratification factors, and the visit-by-treatment group interactions, as well as the continuous, fixed covariate of baseline log-transformed uPCR. As the primary estimate, the difference between treatment groups using a composite contrast of equal-weighted average over weeks 24, 25, and 26 will be estimated (refer to sample SAS code section for more details) with its 95% CI and corresponding p-value. Further details on the presentation of the results are described in Section 6.1above. In addition, the geometric means and geometric mean ratios relative to baseline will also be presented after converting the log-transformed values back to the original unit.

ICEs strategy and handling are listed in Table 1. Imputation for the non-monotone missing pattern (ie, arbitrary missing pattern) will be performed prior to the multiple imputation for the monotone missing pattern (ie, where a missing uPCR measurement at a visit for a participant implies that uPCR measurements at all subsequent visits for that participant are missing).

For the non-monotone missing pattern, missing value(s) between two visits with uPCR measurements will be imputed using the MCMC method based on the MAR assumption, which was first proposed by Li (1988) and Liu (1993) described the algorithm. Multiple imputation will then be carried out for monotone missing pattern. For ICEs due to renal replacement therapy (dialysis and/or renal transplant), missing data will be imputed based on the worst change of all participants across visits plus a random error. For other ICEs, missing data will be imputed based on copy reference imputation:

- Participants with monotone missing data in the placebo arm will have missing data imputed based on the observed values in the placebo arm.
- For the active treatment arm, participants with monotone missing data due to prohibited medication, rescue therapies, or treatment discontinuation will have missing data imputed based on the placebo arm.
- For the active treatment arm, participants with monotone missing data that are not due to prohibited medication, rescue therapies, or treatment discontinuation will have missing data imputed based on the observed values in the active treatment arm.

The number and percent of participants without monotone missing data (separated further by non-monotone missing vs. complete data), the number of participants with monotone missing data and a breakdown of reasons will be reported.

The imputation method will be implemented in SAS using the three standard steps to generate inference from imputed data: imputation step, analysis step, and pooling step. The randomization seed to be used is CCI.

- The missing data are filled in 100 times to generate 100 complete datasets.
- The 100 complete datasets are analyzed by using the MMRM approach described above.
- The results from the 100 complete datasets are combined for inference using Rubin's rule.

The observed values for uPCR will be summarized by treatment group and visit. Summaries will present the descriptive statistics for baseline, absolute values, change and percentage change from baseline data by visit.

The mean change from baseline in uPCR (±SE) will be plotted over time by treatment group. All uPCR data will be listed for the ITT set.

6.4.2. Sensitivity Analyses of Primary Efficacy Endpoint

Sensitivity analyses will be performed to evaluate the robustness of the primary analysis results. Analyses will be performed for the overall population based on the outcome of the primary analyses including all participants in the ITT set.

The following sensitivity analysis will be performed, as appropriate, using the same statistical approach as the one used in the primary analysis:

- Imputation based on MAR: Participants with missing data, regardless of the reason being the ICEs or not, will be handled implicitly within the MMRM analysis under the assumption of missing at random (MAR).
- Tipping point analysis: Participants with a monotone missing data pattern due to the ICEs will have missing data after the last assessment explicitly imputed by multiple imputation using a tipping point analysis method assuming missing not at random (MNAR).

The tipping point analysis method (a delta-adjusted stress testing approach) will be implemented for the active treatment arm under the MNAR assumption by searching for a tipping point that reverses the conclusion regarding positive treatment effect (O'Kelly and Ratitch 2014). The following strategy will be used:

- For the control arm, participants will have missing data imputed based on the observed values in the control arm.
- For the active treatment arm, participants with monotone missing data that are not due to the ICEs will have missing data imputed based on the observed values in the active treatment arm.
- For the active treatment arm, participants with monotone missing data due to the ICEs will have missing data imputed based on the available values (observed values and values imputed for non-monotone missing data) in the active treatment arm with a shift parameter added to the imputed values. Multiple imputation will be implemented with the shift parameter allocated to the missing data point(s) proportionally across timepoints. (eg, for a shift parameter of 0.26 at week 26, incremental shifts of 0.04 would apply to week 4, ..., and week 24, respectively, then a shift of 0.01 would apply to week 25 and week 26, respectively. 0.04 × 6 visits+ 0.01 × 2 visits= 0.26) The range of the shift parameters will be from 0.13 to 0.65 by increments of 0.13 for week 26. A tipping point may not exist within reasonable clinical assumptions.

To generate inference from imputed data, the same three standard steps as described in the main analysis will be implemented.

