17.2. Sample SAS code

```
* The SAS codes in this section are shown as examples
* Some modifications (such as variables used in the model statement)
* may require further changes to reflect the methods specified in the
* SAP and analysis data structure
```

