**if there are ICEs of renal transplant/dialysis (ICEDT2>.) then need to
impute based on worst change;
** first, transpose the above upcr t cbp back to long format upcr cbp(omit
the details), then, collect details on worst percentage across all visits
based on original data (e.g., name the variable as worstpchg), also, identify
for those subjects who had ICEDT2>., their first visit that should be imputed
based on worst percent change (e.g., name the variable as startavisit), plus,
for all 100 imputations, calculate the average log(uPCR) for each avisit
(e.g., name the variable as visit_avg), then;
data upcr cbp worst;
      merge upcr cbp worstpchg startavisit visit avg;
      by subjid;
      if avisitn>startavisit>. then aval = base*(1+ worstpchg/100) + (aval-
visit avg);
      **Note, the "base*(1+ worstpchg/100)" part is worst change, the "(aval-
visit avg)" is random error;
      run;
** lastly, transpose it back to the wide format;
```

```
proc transpose data= upcr cbp worst out= upcr t cbp worst (drop= NAME
_LABEL_) prefix=V;
by usubjid stra1 stra2 distype immunobl trtpn base;
id avisitc;
var aval;
run;
*******************
*** Delta-Adjusted Pattern Imputation (tipping point analysis) ***;
************************
**First identify the subjects in the active treatment groups that we want to
apply the shift parameter if they have monotone missing data;
data upcr t mono2;
     set upcr t mono;
     **ICEDT1=. is just an example of a reason that we do not want to
 apply the shift parameter. The actual reasons are in the text;
     if ICEDT1=. then flag = 1;
     else flag = 0;
     if trtpn = 1 and flag = 0 then adjustthis = 1;
     else adjustthis = 0;
run:
proc mi data=upcr t mono2 out=upcr t tip nimpute=1 seed=
by imputation;
class trtpn adjustthis;
var stra1 stra2 distype immunobl trtpn v00 -- v12;
monotone reg(/details);
mnar adjust(v04 / shift=0.04 adjustobs=(adjustthis = '1' ))
 adjust(v08 / shift=0.04 adjustobs=(adjustthis = '1'))
 adjust(v12 / shift=0.04 adjustobs=(adjustthis = '1' ))
 adjust(v16 / shift=0.04 adjustobs=(adjustthis = '1' ))
 adjust(v20 / shift=0.04 adjustobs=(adjustthis = '1'))
 adjust(v24 / shift=0.04 adjustobs=(adjustthis = '1'))
 adjust(v25 / shift=0.01 adjustobs=(adjustthis = '1'))
 adjust(v26 / shift=0.01 adjustobs=(adjustthis = '1'));
run;
***************
*** SAS macro to run MIANALYZE on outputs from MMRM *;
*****************
%macro mi results(in, lsm, dif); ** Note this macro is for individual visits

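### The primary endpoint's tipping-point search stops at an unexplained shift of 0.65, and less than that may reach the weeks 24–26 contrast

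*SAP*

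**What the plan says.** SAP 6.4.2 lists two sensitivity analyses of the primary endpoint: an MMRM under missing at random, and a delta-adjusted analysis described as "searching for a tipping point that reverses the conclusion regarding positive treatment effect". In the second, active-arm participants with monotone missing data due to intercurrent events (ICEs) are imputed from the active arm and a shift is added. "The range of the shift parameters will be from 0.13 to 0.65 by increments of 0.13 for week 26". The only remark on the limits of the search is "A tipping point may not exist within reasonable clinical assumptions".

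The shift is spread over visits, with the "shift parameter allocated to the missing data point(s) proportionally across timepoints". The single worked example is a shift of 0.26 for someone missing from week 4 onward. The code in SAP 17.2.2 enters each visit's own increment, for example "adjust(v26 / shift=0.01 adjustobs=(adjustthis = '1", identically for every flagged participant. SAP 17.2 adds the caveat "The SAS codes in this section are shown as examples".

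The primary analysis (SAP 6.4.1) treats these participants differently. Active-arm data missing because of prohibited medication, rescue or "treatment discontinuation will have missing data imputed based on the placebo arm". After renal replacement therapy, "missing data will be imputed based on the worst change of all participants across visits plus a random error".

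**The concern.** A tipping-point analysis is useful because it reports how far the missing-data assumption must move before the conclusion fails, so that readers can judge whether that distance is plausible. A grid with an unexplained upper end may finish without a tip, and the SAP does not say what follows if it does. This is the only delta-adjusted analysis of the primary endpoint.

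Two further features weaken it. Because the shift is built up over visits, a participant who drops out late may receive much less than the nominal value. And because it restarts from active-arm imputation, the top of the grid is not automatically harsher than the primary analysis it is meant to stress. At stake is what the sensitivity analysis can tell the reader; the primary estimate and type I error do not change.

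**Working it through.** **Inputs.** Planned reductions of 60% and 20%, SD 0.88 and 35 per arm come from SAP 3.4; 39 per arm is the 78 in the same section. 62 per arm is half of the 124 enrolled (Protocol, amendment summary of changes). The two-sided 0.05 level is from SAP 6.2 and the weeks 24–26 contrast from SAP 6.4.1. The ICE-related imputed share f of the active arm is not in the documents. I use 10%, borrowed from planned attrition, and show 5% and 20%.

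**1. The plan's own figures.** 6 × 0.04 + 2 × 0.01 = 0.26, so the worked example adds up. With a difference of 0.70 and SD 0.88, 35 per arm gives 90.7% power (t), consistent with at least 90%. Unrounded, the planned effect is ln 0.8 − ln 0.4 = 0.693. exp(0.65) = 1.92.

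**2. Shift reaching the contrast at the cap.** Scaling the example to 0.65 gives increments of 0.10 at weeks 4–24 and 0.025 at weeks 25 and 26.
- Missing from week 4, accumulating one for one: (0.600 + 0.625 + 0.650)/3 = 0.625.
- First missing at week 24, fixed increments: (0.100 + 0.125 + 0.150)/3 = 0.125.
- First missing at week 24, full 0.65 rescaled over the three missing visits in ratio 4:1:1: (0.433 + 0.542 + 0.650)/3 = 0.542.

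**3. Carry-over in the code.** The code adds each visit's increment to a sequential regression imputation, so earlier shifts pass forward only through regression coefficients. With an assumed first-order autoregressive correlation of 0.87 per four weeks, the week 24 shift for someone missing from week 4 is 0.10 × (1 − 0.87⁶)/(1 − 0.87) = 0.436, and the weeks 24–26 average is 0.45. With compound symmetry at 0.6 it is 0.18. A correlation of 0.9 per four weeks gives 0.48, still short of 0.625.

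**4. Against the primary's imputation.** For an active-arm participant with no post-baseline value, at the planned effect, copy reference moves the imputed mean by the full 0.693. The cap moves it by at most 0.625.

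**5. Which results the grid could reverse.** SE = 0.88 × √(2/n) = 0.2104 (35 per arm), 0.1993 (39) and 0.1581 (62). Lowest reversible unshifted p ≈ 2[1 − Φ(1.96 + f × 0.625/SE)], with full accumulation from week 4 and SE held fixed:

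| f | 35 per arm | 39 per arm | 62 per arm |
|---|---|---|---|
| 5% | 0.035 | 0.034 | 0.031 |
| 10% | 0.024 | 0.023 | 0.019 |
| 20% | 0.011 | 0.010 | 0.006 |

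These bounds are approximate. A simulation with multiple imputation and Rubin's rules at about 10% saw reversals from p as low as 0.018 (39 per arm) and 0.015 (62 per arm).

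**6. Shift needed to tip at the planned effect.** Shifting a fraction f of one arm by d adds f(1 − f)d² to that arm's variance, which matters once d is large. Solve 0.693 − f·d = 1.96 × √[(2 × 0.88² + f(1 − f)d²)/n]:

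| f | 35 per arm | 39 per arm | 62 per arm |
|---|---|---|---|
| 10% | 2.24 (9-fold) | 2.41 (11-fold) | 3.08 (22-fold) |
| 20% | 1.25 (3.5-fold) | 1.34 (3.8-fold) | 1.70 (5.5-fold) |

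Check at 62 per arm, 10%: 0.693 − 0.308 = 0.385, and 1.96 × √[(1.549 + 0.854)/62] = 0.386.

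**The case against.** The strongest reply is that the grid's insensitivity comes mainly from how little data would be imputed. Measured values after treatment discontinuation are used as they stand, and Protocol 7.3.1 encourages those who stop treatment to complete the remaining visits, so the shifted group may be small. If tipping needs a 9-fold or larger rise in uPCR, the SAP's caveat that no tip may exist is reasonable. The cap is not trivial either: −0.92 + 0.65 = −0.27, a 24% reduction, close to the 20% assumed on placebo. The primary analysis already uses placebo-based and worst-change imputation, so robustness does not rest on this grid alone. The worked example and the code also agree on fixed per-visit increments.

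Most of this stands, and it limits the point. It does not supply the missing rationale for 0.65, and a large tipping delta is evidence of robustness only if it is reported. If fixed increments are intended, late dropouts receive the least shift.

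Three stronger inferences are tempting, and the documents do not support them. One is that the primary result is fragile; nothing here shows that. Another is that only p-values between 0.02 and 0.05 could ever reverse; that band depends on an assumed 10% share and on SD 0.88. The third is that the grid is milder than the primary analysis for everyone. That comparison holds for participants with no post-baseline value at the planned effect; for others it depends on the allocation reading, the correlation and the time course of the effect.

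**Conclusion.** The point holds as a shortcoming of the sensitivity analysis. The cap of 0.65 is unexplained and slightly below the planned difference. The nominal shift is not reliably delivered on the primary contrast: at most 0.625; for first missingness at week 24, 0.125 or 0.542 under one-for-one accumulation; and about 0.18–0.45 even from week 4 if the example code's increments carry forward only by regression, under the correlations assumed. The stated tipping strategy also does not carry over the worst-change rule after renal replacement.

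A report of no tip up to 0.65 would therefore leave the degree of robustness unknown. The p-value bounds and tipping deltas are illustrations that depend on the unknown imputed share, SD 0.88 and 35–62 per arm. The change should be made, but it is not critical.

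**What to change.** In SAP 6.4.2:
- Apply the full delta to every ICE-related missing week 24, 25 and 26 value in the active arm, and make the code deliver it. The printed example also needs its variable list extended, since it ends at v12 while the shifts run to v26.
- Increase delta until the two-sided p exceeds 0.05.
- Report the tipping delta on the weeks 24–26 contrast scale and as a uPCR fold-change, beside the number of participants shifted. SAP 6.4.1 already plans counts and reasons for monotone missingness.
- Add one run that starts from the primary's own imputation: copy reference, with worst change kept after renal replacement.

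The 0.13–0.65 grid can stay alongside, with a sentence justifying its upper end. The cost is SAP wording and a longer programming loop; no new data or participants are needed.
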